- Positional change of bending over to evaluate 'bendopnea' (shortness of breath symptoms with bending over).

Phone Call

Subjects will be contacted by study team six months (\pm 14 days) following their nerve block procedure. The purpose of this call will be to obtain mortality status and document the number of inpatient admissions since the procedure.

Blood samples processing:

Some blood samples collected before and after the nerve block (plasma metanephrines, plasma catecholamines, angiotensin II and arginine vasopressin) will be processed (centrifuged) and stored at -70 degrees Fahrenheit before sent out to an external lab. Storage duration may vary between weeks to months. Samples will be stored in a research freezer located on the 7th floor of Duke North (cath lab research freezer). As part of the study, we will send blood for study-related laboratory tests to the Mayo clinic and Inter Science Institute. These would include laboratory tests such as metanephrines, vasopressin, catecholamines, and angiotensin.

Safety endpoints:

- The duration of the anesthetic block is estimated for 1.5 hours. The subject will be monitored for up to 1.5 hours in the catheterization laboratory (acute safety). Chronic safety up to 48 hours post procedure. Hereby the patient will be observed clinically on the floor or CCU per standard clinical care routine. Further the subject's medical chart will be observed for 6 months following study enrollment to evaluate for recurrent admissions for heart failure.

Incidence of major side effects like:

- Pneumothorax, possibly requiring a chest tube
- Aortic puncture with retroperitoneal bleed or hematothorax
- Spinal cord trauma with possibly paralysis

Incidence of minor side effects like:

- Orthostatic hypotension
- Pain at puncture site and intercostal neuralgia

- Gastrointestinal dysmotility including diarrhea, constipation and abdominal cramping
- Bleeding at puncture site

Efficacy endpoints:

The following efficacy endpoints will be evaluated:

- Primary: Reduction in central venous pressure and/or pulmonary artery pressure (diastolic) and/or pulmonary capillary wedge pressure at 30-60 minutes after nerve block
- Secondary: Increase in cardiac output, improvement in echocardiographic parameters like ejection fraction (increase), central venous pressure (decrease), pulmonary artery systolic pressure (decrease), right ventricular diameter (decrease), left ventricular diameter (decrease)

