Other minor risks include (in order of report in literature and experience at Duke):

- Pain at puncture site and intercostal neuralgia
- Gastrointestinal dysmotility including diarrhea, constipation and abdominal cramping as well as nausea
- Bleeding at puncture site

We will perform the splanchnic block for heart failure, which is a new indication. The splanchnic nerve block has not been studied in the setting of this disease. While we don't expect unexpected side effects other than stated above, unexpected side effects cannot be excluded. For safety purposes patients enrolled in this study will remain hospitalized for at least 48 hours (part of enrollment criteria). This way they will be closely monitored while admitted on a cardiology floor/unit.

Anticipated benefits to the patient include improvement in central vascular congestion with a reduction in cardiac preload and pulmonary arterial pressures as well as left sided filling pressures. A reduction in cardiac pressures is also likely to improve symptoms of congestion, including shortness of breath.

Further it is expected that a decongestion of the central veins and interruption of the cardiorenal reflex loop will result in an improvement in renal function as measured by urine output. This will further contribute to the decongestion of the subject's vasculature.

While both of those effects are only temporary, the benefit provided by the brief episode of decongestion can provide lasting symptomatic improvement. Our intervention serves an additional diagnostic purpose by confirming an increased sympathetic tone in the abdominal innervation and could prompt the treatment team to adjust medical therapy to address the increased sympathetic tone and possible benefit on increased splanchnic capacitance.

11. Costs to the Subject:

The study will be at no additional cost to the patient on top of his regular hospitalization for heart failure and elective catheterization.

12. Data Analysis & Statistical Considerations:

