Descriptive statistics of continuous outcomes will include sample size, mean, median, standard deviation, minimum and maximum. For categorical outcomes, the number and percentage of subjects in each category will be presented. Statistical comparisons will be made using t-tests for continuous outcomes and chi square or Fisher's exact test (depending on overall event rates) for categorical outcomes. Paired t-tests will be used to compare changes from baseline to post-intervention. All statistical analyses will be performed using SAS for Windows (version 8.2 or higher) or other widely accepted statistical or graphical software. Patient data listings and tabular and graphical presentations of results will be provided. Unless otherwise specified, a two-sided 0.05 level of significance will be used to declare change in pre- and post-procedure variables different.

For power analysis, our primary endpoint is decreased in central venous pressure following nerve blockade. Based on preliminary animal experiments, we anticipate a reduction of CVP of 25%. For a sample size of 16, If the true difference in the experimental and control means is 25%, we will be able to reject the null hypothesis that the population means of the experimental and control groups are equal with probability (power) .90. The Type I error probability associated with this test of this null hypothesis is 0.05.

There is no direct measure of technical success following attempted block of the splanchnic nerves. The location of the splanchnic nerves is estimated biased on human anatomy dissections and established nerve block protocols used by the anesthesiology department. Procedural success to block the splanchnic nerves will be assumed in 70% of the cases based on the experience in splanchnic nerve blocks in patients with intractable cancer.

13. Data & Safety Monitoring:

Due to the experimental nature of this intervention, data will be recorded after each subject completes the intervention for signs of unintended negative effects. These include hypotension, worsening renal function, or clinical deterioration. Additionally, patient's electronic medical data will be clinically screened for any traumatic complications from the nerve block for the first 24 hours postprocedure.

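### The incidence of gastrointestinal dysmotility, puncture-site pain and intercostal neuralgia is a safety endpoint, but no scheduled assessment asks about them before or after the block

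*Combined protocol and SAP*

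**What the plan says.** Section 4, under Safety endpoints, lists minor side effects whose incidence is to be evaluated. Two entries matter here: "Pain at puncture site and intercostal neuralgia" and "Gastrointestinal dysmotility including diarrhea, constipation and abdominal cramping". The window and the method follow from the same heading: "Chronic safety up to 48 hours post procedure", and "Hereby the patient will be observed clinically on the floor or CCU per standard clinical care routine".

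Section 13 adds two study-level activities. First, "data will be recorded after each subject completes the intervention for signs of unintended negative effects", with the explanation "These include hypotension, worsening renal function, or clinical deterioration". Second, the subject's "electronic medical data will be clinically screened for any traumatic complications from the nerve block for the first 24 hours" after the procedure. Section 13 also sends other adverse events to the IRB and provides for an annual report of side effects.

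Section 10 describes heart failure as a new indication for this block and notes that "patients enrolled in this study will remain hospitalized for at least 48 hours". Its list of other minor risks, ordered by how often they are reported, puts puncture-site pain with neuralgia first and gastrointestinal dysmotility second, and adds nausea to the latter.

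**The concern.** An incidence needs a defined way of finding cases: who asks or looks, when, and against what starting point. For these symptoms the plan defines none of the three. The trial is uncontrolled, so each subject's own pre-block status is the only comparator, and for these symptoms it is not recorded.

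Two errors can follow, and they pull in different directions. A subject with mild cramping or chest-wall pain may never mention it, or nobody may chart it, which lowers the count. A subject who was already constipated before the block may be charted as constipated afterwards and counted as a case, which raises it. Section 12 would then report a number and percentage that readers would take as the side-effect rate of the block in a population where, by the protocol's own account, it has not been studied.

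**Working it through.** **Step 1. Compare the endpoint list with what is scheduled.**

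| Minor side effect (Section 4) | Study measure before block | Study measure after block |
|---|---|---|
| Orthostatic hypotension | Orthostatic vitals, study-specific | Orthostatic vitals, study-specific |
| Puncture-site pain, intercostal neuralgia | None | None scheduled; might fall under the chart screen, since the term traumatic is not defined |
| Diarrhea, constipation, abdominal cramping | None | None scheduled; not naturally covered by the chart screen |
| Puncture-site bleeding | Not applicable | Plausibly covered by the chart screen |

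The only symptom questionnaire is for dyspnea (7-point Likert and visual analog scales). The leg-raise and bending tests also concern shortness of breath. The plan thus measures one listed minor side effect actively on both sides of the block, but not the two entries at issue.

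**Step 2. Compare the windows.** Safety observation runs to 48 hours (Section 4), while the chart screen runs to 24 hours (Section 13). The second 24 hours have ward observation but no defined study review of the record for complications.

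**Step 3. Is there a figure to reproduce?** No. The documents give no expected incidence for these events and no detection rate. What follows is illustration with assumed values; only n = 20 (the Section 5 target of up to 20) comes from the plan.

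**Step 4. Effect of incomplete capture alone.** Let p be the true incidence and s the share of events recorded. The expected recorded rate is p × s, and the chance of recording none in 20 is (1 − p × s)^20.

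| Assumed s | p = 20%: recorded rate | p = 20%: chance of none | p = 10%: recorded rate | p = 10%: chance of none |
|---|---|---|---|---|
| 100% | 20% | 0.80^20 = 1.2% | 10% | 0.90^20 = 12.2% |
| 75% | 15% | 0.85^20 = 3.9% | 7.5% | 0.925^20 = 21.0% |
| 50% | 10% | 0.90^20 = 12.2% | 5% | 0.95^20 = 35.8% |
| 25% | 5% | 0.95^20 = 35.8% | 2.5% | 0.975^20 = 60.3% |

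With 0 events recorded in 20, the exact two-sided 95% upper limit for the recorded rate is 1 − 0.025^(1/20) = 16.8%. Dividing by s gives the corresponding limit for the true rate: 16.8% at s = 100%, 33.7% at 50% and 67.4% at 25%. These limits treat s as known and simply carry the assumption through.

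**Step 5. Effect of the missing baseline.** Suppose a share b of subjects unaffected by the block already have the symptom, and that it is recorded and counted with the same share s. The expected recorded rate becomes s × [p + (1 − p) × b]. It equals p when b = p × (1/s − 1)/(1 − p). With p = 20%:

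- s = 50%: b = 0.20 × 1/0.80 = 25%.
- s = 25%: b = 0.20 × 3/0.80 = 75%.

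Below these values of b the recorded rate is too low; above them it is too high. The documents give neither s nor b, so the net direction is not fixed.

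**The case against.** A reader might infer that the review looks only for trauma and circulatory or renal signs, cannot detect gastrointestinal or neuralgic symptoms, and will therefore report too low an incidence. The text does not support that reading.

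- Section 13 records unintended negative effects in general. Its list is given as examples, and clinical deterioration is not confined to the circulation or the kidney. The chart screen is an addition, not the sole method.
- Subjects are inpatients for at least 48 hours and meet study staff for questionnaires, walk tests, orthostatic vitals and timed voids. A complaint can be volunteered at any of these and then falls under adverse-event reporting.
- Puncture-site pain and neuralgia after needle placement could be read as traumatic complications.
- The missing baseline can inflate the count, so a downward error is not certain.
- Section 10 describes the risks as uncommon and the mild ones as time limited, and this is a small proof-of-concept study with no hypothesis test specified for safety.

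All of this stands against the stronger reading. It does not supply a method of ascertainment. The IRB routes govern events already known, not how they are found. An open list of examples instructs nobody to ask. Contacts at which a subject might speak up are not a collection procedure. A wide reading of traumatic would still leave out diarrhea, constipation and cramping. None of these points provides a pre-block value.

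**Conclusion.** The point holds as a gap in ascertainment. The plan names these incidences as safety endpoints but schedules no question about them before or after the block, and its one defined chart screen is narrower than the endpoint list and covers 24 of the 48 hours. Detection is passive. Mild events may be missed, and recorded ones cannot be attributed to the block rather than to symptoms already present.

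The conclusion stops there. Under-counting is a risk, not a demonstrated result, and neither the size nor the net direction of the error can be derived from the documents. The capture shares, true rates and resulting limits above show only how sensitive a sample of 20 is to the method of collection. The finding itself rests on the schedule and Section 13 as written, with no assumption beyond taking the Table of Assessments and the procedure lists as the full set of study assessments. The events are minor, but they are named endpoints in a new indication, and a missing pre-block record cannot be reconstructed later. The change is worth making.

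**What to change.** 1. Add a short yes/no checklist at three dyspnea-questionnaire contacts that already exist: same day before the procedure, 12-24 hours after the block, and 48 hours. Cover diarrhea, constipation, abdominal cramping, puncture-site pain, intercostal neuralgia and puncture-site bleeding from Section 4, plus nausea, which appears only in Section 10. The puncture-site items apply after the block only. Orthostatic hypotension already has its own measurement.
2. Define a case as a symptom that is new or worse than before the block, and report the number and percentage on that definition. State who administers the checklist.
3. In Section 13, widen the chart screen from traumatic complications to all side effects listed under Safety endpoints, and run it through the 48-hour window so that the two sections agree.

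Cost: about a minute at each of three contacts, with no added visit, staff or procedure, and a somewhat longer chart review. Asking directly may change the reported minor event rates and will probably raise them, although the new-or-worse rule works the other way. The report should state that symptoms were solicited, so that the rates are not set against spontaneously reported ones without comment.

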2. Bilateral splanchnic nerve block performed by an anesthesiologist (see images below) (CS). Following the right heart catheterization procedure the patient will be prone on the abdomen. Central venous access remains in place. Needle will be placed under fluoroscopic guidance in the posterior chest wall. Anesthetic solution (1% lidocaine with epinephrine) (1:200.000) will be injected (10-15 ml on each side). Patient will then be placed back on his/her back and central

hemodynamics are recorded again for the next 1-1.5 hours, approximately every 15 minutes. The central venous catheter will be removed after the hemodynamic monitoring is completed in the catheterization laboratory. Unless the primary team requested the catheter to remain in place and the patient is moved to the intensive care unit.

Following the block, the subject will repeat the positional change of a leg raise at 30, 60, and 90 minutes post-block to observe any changes in shortness of breath symptoms.

Additional measurements include:

- Orthostatic vitals will be obtained at the end of the hour while in the catheterization lab (CS).
- Dyspnea questionnaire (CS)
- If medically indicated a Swan Ganz catheter will be left in place. This would enable continuous monitoring of central hemodynamics for the next 24h (q4h) (SOC).

Follow up procedures:

Following right heart catheterization and lidocaine splanchnic nerve block the patient will be monitored on the floor/CCU for at least 48 hours following nerve block (SOC).

- Continuous recording of urine output for 24 hours (SOC). They will then be asked to void again 3 and 8 hours after the placement of the nerve block and 24 hours after nerve block (CS).
- Basic vitals (SOC) and orthostatic vitals (CS) within 24 hours after nerve block, and record heart rate variability using a non-invasive wrist monitor (CS).

- Repeat labs 12-24 hours after nerve block (next morning) [BUN (SOC), BMP (SOC) and pro-BNP (CS)
- Labs: Angiotensin 2, plasma metanephrines (if on inotropes), plasma catecholamines, vasopressin and urine sodium will be collected immediately before and after the procedure
- Dyspnea questionnaire at 12-24 hours after nerve block (CS) and again at 48 hours
- Six minute walk test (CS) within 24 hours after block and again at 48 hours
- Weight the next morning after nerve block (SOC) and at 48 hours.
- Echocardiogram within 1-2 hours after nerve block (CS)

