 - Reduction in pro brain natriuretic peptide (pro-BNP)
 - Increase in UOP (output measured in ml/hour) and renal function (BUN and creatinine) in the hours following the procedure. Follow up for 48hours
 - Symptomatic improvement like a decrease in dyspnea (dyspnea questionnaire) and 6-minute walk test

5. Selection of Subjects:

Subjects will be recruited from Duke University Medical Center. All potential study subjects are admitted for ADHF and are treated as inpatient on the regular floor or in the intensive care unit.

The study will enroll subjects who meet the criteria as detailed below. Potentially eligible patients will be consented and entered into a screening process, which will include a chart review and physical examination. The primary enrollment target is up to 20 subjects (10 HF with preserved ejection fraction and 10 HF with reduced ejection fraction).

Inclusion criteria:

- Age 18-90
- Established diagnosis of HFpEF or HFrEF
- Admitted to DUMC for decompensated HF (NYHA stage 3-4, Class C-D), including patients on inotropic medication
- Symptomatic with dyspnea with clinical, radiographic or echocardiographic signs of fluid overload
- Planned for elective diagnostic right (+/- left) heart catheterization
- On a stable HF drug regimen prior to admission
- Anticipated hospital stay of at least 2 nights following catheterization procedure

- Preferably "diuretic resistant". Urine output <50ml/hour in the 24 hours preceding enrollment into the study.

Exclusion criteria:

Contraindicated medications:

- Anticoagulation at the time the procedure or in case of recent warfarin use an INR >1.4. Anticoagulation includes: warfarin, or novel oral anticoagulants like dabigatran, rivaroxaban, apixaban, endoxaban or full dose intravenous heparin products or bivalirudin and fondaparinux). Antiplatelet agents besides aspirin such as ticagrelor, prasugrel, Plavix are also considered to be a contraindication if used at time point of procedure.
- Immunosuppressive medications for solid organ transplant

HF medication regimen:

- Initiation of HF medications (in the 48 hours preceding the study) such as beta blockers, ACEI, ARB, aldosterone receptor blockers, calcium channel blockers of any type, central sympatholytics like clonidine, moxonidine,

- Recent acute MI or hemodynamic instability:

- Acute MI (STEMI or Type I NSTEMI) within 7 days?
- Evidence of progressive cardiogenic shock within 48 hours
- Repeat systolic blood pressure <90mmHg or >180mmHg

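### The record screen for traumatic block complications ends at 24 hours, but the safety endpoint runs to 48 hours, so capture in the second 24 hours is left to routine care

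*Combined protocol and SAP*

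**What the plan says.** **Endpoint window.** Section 4, under Safety endpoints, separates an acute period of up to 1.5 hours in the catheterization laboratory from a longer one: "Chronic safety up to 48 hours post procedure". It then says how the longer period is observed: "Hereby the patient will be observed clinically on the floor or CCU per standard clinical care routine". The same heading lists the major side effects whose incidence is to be evaluated: pneumothorax, "Aortic puncture with retroperitoneal bleed or hematothorax", and spinal cord trauma. No separate, shorter window is given for them.

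**Study screen.** Section 13 says that "data will be recorded after each subject completes the intervention for signs of unintended negative effects", naming hypotension, worsening renal function and clinical deterioration, with no end time. It adds a further step for needle trauma: the electronic record is to be "screened for any traumatic complications from the nerve block for the first 24 hours postprocedure".

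**Length of stay.** Section 4, Follow up procedures, states that "the patient will be monitored on the floor/CCU for at least 48 hours following nerve block (SOC"). Section 10 says that "patients enrolled in this study will remain hospitalized for at least 48 hours (part of enrollment criteria"). The criterion in Section 5 reads: "Anticipated hospital stay of at least 2 nights following catheterization procedure".

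**The concern.** The major events in the safety endpoint are the traumatic complications of the block. The one step in the plan that looks for them systematically stops halfway through the window that defines the endpoint. An event first documented on the second day would enter the study data only if routine care found it and someone passed it on, and the plan does not say how that happens.

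This matters because Section 10 describes a new indication in which the block has not been studied and unexpected effects cannot be excluded. The sample is small, so one event more or less changes the reported incidence visibly. A figure labelled as 48-hour incidence but built on a 24-hour screen would also be hard for a reader to interpret.

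The stay wording adds a smaller problem. Section 10 attributes a 48-hour stay to the enrolment criteria, but the criterion is a forecast expressed in nights.

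**Working it through.** The plan gives no figure to reproduce here. The check compares stated time windows, followed by simple arithmetic.

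**1. Screen against endpoint**

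- Endpoint window (Section 4, Safety endpoints): 48 h.
- Record screen for traumatic complications (Section 13): 24 h.
- Window without a stated screen: 48 − 24 = 24 h, and 24/48 = one half.

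**2. Does another stated procedure capture these events in hours 24 to 48?**

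| Source | What it provides | States capture of traumatic events in hours 24–48? |
|---|---|---|
| Section 4, Safety endpoints | Clinical observation to 48 h under standard care | Observation yes; no study recording step |
| Section 4, Table of Assessments, 48 h column | Vitals, weight, urine output, metabolic panel, dyspnea questionnaire, heart rate variability | No; the table has no adverse event or complication row |
| Section 13, recording after the intervention | Hypotension, worsening renal function, clinical deterioration; no end time | Not specifically; trauma is handled in the separate 24-hour sentence |
| Section 13, IRB reporting | Deadlines of 24 hours or 10 working days, plus an annual report | No; these apply once an event is known |
| Sections 4 and 13, later chart review | Heart failure readmissions | No |
| Section 4, six-month call | Mortality status and number of admissions | No |

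None of these states how a traumatic event first documented after 24 hours reaches the study dataset.

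**3. Effect of one missed event on the incidence**

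The shift is 1/n, where n is the number of subjects who receive the block.

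- n = 20 (upper enrolment target, Section 5): 1/20 = 5 percentage points.
- n = 16 (sample size in the Section 12 power statement): 1/16 = 6.25 points.

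Section 4 withholds the block from patients whose hemodynamics do not show decompensation, and enrolment is up to 20. So n is at most 20 and the shift is at least 5 points.

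**4. Two nights expressed in hours**

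Hours from block to discharge = 48 + (discharge clock time on the second day after the block − clock time of the block).

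The documents give no clock times; Section 4 allows both early morning and afternoon cases. *Assumed* ranges: block between 09:00 and 17:00, discharge between 08:00 and 16:00.

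- Shortest: 48 + (8 − 17) = 39 h.
- Longest: 48 + (16 − 9) = 55 h.
- An afternoon example, 15:00 to 11:00: 48 + (11 − 15) = 44 h.

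Under these assumptions a two-night stay can fall up to 48 − 39 = 9 h short of 48 hours, mainly after an afternoon block. Early morning cases usually reach 48 hours.

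**The case against.** The strongest reply is that the second day is watched. Section 4 commits to at least 48 hours of monitoring on the floor or CCU, counted from the block, and Section 10 repeats the 48-hour stay. Study-specific data are collected at 48 hours. The 24-hour screen is introduced as an addition to other monitoring, and Section 13 records clinical deterioration without an end time. Adverse event reporting to the IRB has no limit on when the event occurs. A serious event in an inpatient would probably come to light.

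Most of this stands. A reader might infer that the safety window is not covered, or that patients go unobserved after 24 hours. The documents do not support that, because they commit to 48 hours of inpatient monitoring. Nor do they show that the reported incidence *will* be too low: that needs an event that first appears after 24 hours and escapes both care and reporting, and the plan gives no rate for this.

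What the reply does not supply is a stated step that turns bedside observation into an endpoint count. The plan writes such a step for trauma and ends it at 24 hours. If that cut-off is deliberate, the reason is not given and the endpoint window does not reflect it.

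On length of stay, the reply is fair that an eligibility criterion can only be a forecast, and that the commitment in hours already appears in Sections 4 and 10. What remains is that Section 10 describes the criterion as something it is not.

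**Conclusion.** The inconsistency is real and limited. The dedicated screen covers half of the endpoint window (24 of 48 hours), and for the other half no study-level capture of traumatic events is stated beyond routine care. The 48-hour incidence of major complications could be understated, by at least 5 percentage points for each missed event with at most 20 subjects. This rests on reading the 48-hour window as applying to the listed major events, which is the natural reading because they share a heading and have no other window.

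The stay wording is secondary. Two nights may be about 39 to 55 hours, but only under assumed clock times, and it does not show that any patient would leave early.

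Two further inferences should be avoided. The primary efficacy endpoint is measured at 30 to 60 minutes, so neither it nor the sample size is affected. The imprecision of a zero-event result in 20 subjects is also a separate matter: its upper confidence limit is the same whether the window is 24 or 48 hours.

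**What to change.** In Section 13, extend the record screen for traumatic complications to the 48-hour window that defines the safety endpoint in Section 4. This costs one more day of chart review per subject, in patients who are already meant to be in hospital, and needs no additional test or visit.

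Separately, reconcile the three statements on length of stay: monitoring for at least 48 hours after the block (Section 4, Follow up procedures), the anticipated two nights (Section 5), and the 48 hours described as part of the enrolment criteria (Section 10). This is a wording edit; which stay rule should apply is for the investigators to decide.
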